**NCT 07074171**

**Version Date: 11/07/2024**

**Protocol Template Version July 2024**  
*Adapted from NIH protocol template and ICH Guidelines*

Protocol Title:	Influencing Factors of COVID-19 Testing: Main Study 2024
Principal Investigator:	[name], UTHealth School of Public Health in Houston
Co-Investigators:	[name], UTHealth School of Public Health in Brownsville and Rio Grande Valley; [name], UT Health Science Center at Tyler; [name] UTHealth School of Public Health in Houston, [name], UTHealth School of Public Health in Houston, [name] [name], UTHealth School of Public Health in Houston,
Study Coordinator:	[name], [name], [name]
Population:	431 individuals in the intervention group, Male, Female, 18-89, general population sample drawn from the community through door-to-door outreach and community events in Northeast Texas, Harris County, and South Texas.
Number of Sites:	Three sites: Houston, Lower Rio Grande Valley, and Tyler, UT Houston is the lead site of the multi-site study
Study Duration:	The study will run from July 2024 - February 2025
Subject Duration:	Intervention study participants will be enrolled, complete a baseline survey, and participate in a text message-based educational intervention throughout the study. They will be followed up by phone or in person for 8 weeks. For the control group participants' information, we will use a historical control group (the Control group from the phase II Embedded Study trial that completed a baseline and follow-up survey).

## General Information

RADx-UP is an ongoing research study funded by the National Institutes of Health to address COVID-19 testing disparities in vulnerable populations. The goal of RADx-UP is to reduce the burden of disease in vulnerable populations known to be at increased risk of severe COVID-19 infection (e.g., those with medical comorbidities, homeless, racial/ethnic minorities who live in rural communities). The focus of the Phase I main RADx-UP study was to examine COVID-19 testing to reduce infection transmission and prevalence. There are three sites (Houston, Northeast Texas, and South Texas). The Phase I main study questions were answered (approved under another IRB protocol) in a Randomized Control Trial (RCT) where 120 priority block groups were randomized to one of three conditions: 1) Multi-Level Intervention (MLI) group; 2) Community JITAI (Just-In-Time Adaptive Intervention) 3) Control group. The outcomes of this study were measured at the population level, and no individual data was gathered.

In Phase II, the embedded study was built off this main trial with some adjustments to the design because of expanded research priorities to include factors influencing antigen testing. The intervention priority census block groups (PBGs) that received either form of intervention in the main trial were combined into one pool of intervention PBGs for the embedded study. The control PBGs from the main trial remained the pool of control PBGs for the embedded study. A sample of intervention PBGs were randomly selected from across the three study regions and assigned to one of two intervention study arms. A sample of the control PBGs was randomly selected from across the three study regions and assigned to the control condition. We are recruiting and enrolling individuals from the selected PBGs across the three arms using systematic sampling with a random start.

In Phase III, we will build off of the Phase II embedded study with some adjustments to the design to address new research priorities that examine an intervention that is network informed and delivered through community health worker interactions plus digitally-delivered intervention content with the goal of increasing COVID-19 testing and vaccination. This model, if proven effective, can be scaled up to address COVID-19 and other future pandemics. We will utilize the sample of intervention PBGs used in Phase II and will recruit and enroll participants not previously enrolled in either phase I or II from these PBGs using convenience sampling methods. We will use a historical control group consisting of participants from our control arm in Phase II who completed both their baseline and follow-up surveys embedded in the study.

## **Background Information**

Vulnerable populations in the U.S. experience significant COVID-19 disparities, and individuals with medical comorbidities have suffered disproportionately. Additionally, Hispanics are 1.5x more likely to be infected, 2.3x more likely to be hospitalized, and 1.8x more likely to die from COVID-19 compared to White, Non-Hispanics. Blacks are 2.4x more likely to be hospitalized, and 1.7x more likely to die. The Phase III main study builds on our RADx-UP Phase I and Phase II work reaching these populations in three racially diverse regions: Houston/Harris County, South Texas, and Northeast Texas, leveraging the partnerships and resources of the Center for Clinical and Translational Science (CCTS) to increase SARS-CoV-2 testing, vaccination, and mitigation behaviors to reduce COVID-19 among underserved populations in Texas. The pandemic landscape and people's experiences with testing, infection, and vaccination have changed dramatically over the past two years. Vaccines have become available, testing access in local communities has waxed and waned, and attitudes toward COVID-19 severity and susceptibility have changed.

Antigen self-testing kits are more available at this stage in the evolution of COVID-19, but among vulnerable populations, use is still low, and instructions for antigen testing are not typically designed for low health literacy populations. Navigating the shifting testing-decision landscape is confusing to the public (test availability for free versus charged or requiring insurance; testing and vaccination locations change; PCR versus antigen testing; home tests versus clinically delivered; symptom-based testing, exposure-driven testing, serial testing, resources to trust or not trust, etc.). Studies are needed to explore access and use of antigen tests, including serial testing among vulnerable populations, and studies are needed to examine if low health literacy designed interventions improve COVID-19 testing decisions and completion behaviors.

The proposed study will focus on understanding factors associated with *rapid* SARS-CoV-2 testing, specifically.

## Study Partners

This proposal leverages long-standing community partnerships and resources building specifically on the CCTS community engagement component and other community and organizational partnerships developed through several programs and projects across the three Texas regions. These Community Stakeholder Advisory Groups in each region ensure that bidirectional communication about COVID-19 and the study activities are responsive to community input and deemed culturally appropriate and impactful. Our partnerships, including those with local health departments and hospital systems, have enabled data sharing and analysis of surveillance data. New organizations, such as the UTHealth Institute for Implementation Science and the Texas Epidemic Public Health Institute (TEPHI), will provide additional resources to enhance the proposed study.

## Objectives

The primary objective of this study is to:

- 1) Determine the effectiveness of the adapted MC-NET-JITAI (Multilevel Community network-informed Just-In-Time-Adaptive Intervention) versus a historical control group.

## Study Design:

**RADx-UP Phases I & II.** (The parent studies) We conducted a three-arm group randomized trial to assess the impact of multilevel interventions influencing motivation and access to testing: Arm 1) Community Engaged Just-In-Time Adaptive Intervention (Community JITAI) where we met regularly with community partners and exchanged community-specific information about COVID-19 (testing, infection rates, etc), Arm 2) Standard multilevel intervention (MLI), and a usual practice condition. We randomized 120 PBGs identified as communities with high levels of disparities across our three geographic regions to each condition using a covariate adaptive Randomization (Minimization) Schedule.

The primary outcome for the Phase I and II studies was community-level SARS-CoV-2 testing (primarily PCR testing). This measure was assessed bi-monthly throughout the study. We also conducted an embedded panel study to 1) compare the effectiveness of the CHW-Facilitated Self-Sampling Intervention (FSSI) vs. CHW Testing Navigation Intervention (TNI). In the ongoing study, we also collected social network data on a sub-sample of individuals to explore the influence of social networks on testing decision-making and behavior.

**RADx-UP Phase III:** Our Phase III study design focuses on **vulnerable communities** selected to intervention and control conditions and takes advantage of the fact that these communities were randomized to conditions using methods to ensure balanced arms. In Phase III, we will combine the two intervention conditions (TNI & FSSI), and will receive the MC-NET-JITAI. The study will include PBGs from each of the two intervention conditions in Phase II; they will be matched to the comparison PBGs on variables such as size, vaccination and testing rates, and the disparities index with the control group. The intervention will last 8 weeks; individuals will be recruited and asked to complete a survey (including RADx-UP common data elements).

In Phase III, we will utilize a historical control group consisting of 400 participants from the control arm who completed the baseline and follow-up surveys in the Phase II embedded study.

In Phases I and II, the PBGs were selected from the Harris/South Texas/NE Texas region at the ratio of 2:1:1, that is, 20 PBGs of MC-JITAI arm in Harris, 10 in South Texas, and 10 in NE Texas. Among the 40 PBGs in the control arm, all remain in the control group. During Phase II recruitment, we identified PBGs where recruitment was not feasible due to various factors (ex., dangerous areas, largely gated

neighborhoods, neighborhoods with HOAs that did not permit us entry into the neighborhood, etc.). Recruitment in Phase III will occur only in PBGs where it is feasible to return.

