## Study Procedures

### Sample Selection via Convenience Sampling- Houston/Harris County and Cameron County

Study personnel from the Houston/Harris County & Cameron County areas will prepare for each PBG randomized to the study by mapping all streets in the selected PBG using Google Maps. Study personnel (CHWs) will approach each house as they recruit through the PBG, skipping those homes where current or past Phase II embedded study participants live. The CHWs will work in teams. One member of the team will work one side of the street and the other will work the other side of the street, both following the same sampling protocol. There may be occasions when it is appropriate that both team members work the same side of the street approaching the same houses together. Each attempt, successful or unsuccessful, will be recorded on a tracking sheet with items such as date and time attempted, address, identifying characteristics of households approached, whether individuals fit the inclusion and exclusion

study criteria, whether individuals consented to the study, reason for refusal or no answer, whether the survey was completed, whether Wi-Fi was available and barriers to visiting completion.

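### The earlier randomisation does not give balanced arms for Phase III: the historical-control contrast cannot separate MC-NET-JITAI from carry-over of, or interaction with, earlier community exposure

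*Combined protocol and SAP*

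**What the plan says.** All references are to the combined protocol and SAP.

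- **Where Phase III recruits.** General Information: "We will utilize the sample of intervention PBGs used in Phase II". Study Design: "The study will include PBGs from each of the two intervention conditions in Phase II".
- **What those PBGs had before.** General Information says that, for Phase II, the PBGs that "received either form of intervention in the main trial were combined into one pool of intervention PBGs". A sample of that pool was then assigned to one of two Phase II arms, which Study Design names as TNI and FSSI.
- **What the control PBGs had before.** General Information: "The control PBGs from the main trial remained the pool of control PBGs for the embedded study". Study Design: "Among the 40 PBGs in the control arm, all remain in the control group". It describes the comparison condition as usual practice.
- **The balance claim.** Study Design says that Phase III "takes advantage of the fact that these communities were randomized to conditions using methods to ensure balanced arms".
- **The objective.** The Objectives section sets out to "Determine the effectiveness of the adapted MC-NET-JITAI" against a historical control group.
- **The analysis.** Statistics plans a within-cohort McNemar test, a ratio of odds ratios for intervention versus control, a GLMM on the prospective cohort, and a GLMM on both groups. The fixed effects of that last model are not given. Nothing there addresses earlier exposure or carry-over.

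**The concern.** A randomisation supports a causal contrast between the conditions it assigned. The one cited here assigned the earlier interventions. It made PBGs comparable before Phase I and then created the difference in treatment history that Phase III inherits. Offering it as a strength of Phase III credits the MC-NET-JITAI contrast with a property it does not have.

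The stakes lie in attribution. A favourable ratio of odds ratios could partly reflect communities whose testing was already changing because of Phases I and II, or that respond better to a third round. An unfavourable one could partly reflect a ceiling left by the earlier work. General Information says that the model, if effective, can be scaled up. Evidence drawn only from previously exposed communities does not show what the model does elsewhere.

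**Working it through.** **1. Treatment history by arm.**

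| | Phase III intervention PBGs | Historical-control PBGs |
|---|---|---|
| Phase I | MLI or Community JITAI | usual practice |
| Phase II | TNI or FSSI | control |
| Condition compared | MC-NET-JITAI | control (Phase II survey data) |

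The plan has no previously exposed PBG without MC-NET-JITAI and no unexposed PBG with it. Aliasing is complete, so no model fitted to these two groups can separate the two factors.

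**2. The plan's own figure.** An exact one-sided McNemar test at 2.5%, with odds ratio 2.5 and discordance 0.19, first reaches 80% power at n = 237 (power 0.8001). Enrolment is 237 / (1 - 0.45) = 430.9, rounded up to 431. Both agree with the sample-size section. The calculation uses no control group, so this point does not touch it.

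**3. What the ratio of odds ratios removes.** On the log-odds scale, write:

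- control change = trend
- intervention change = trend + ln(MC-NET-JITAI effect) + ln(k)

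Here k is the factor by which earlier exposure alters the 8-week change. A shift in testing level present equally at baseline and follow-up appears in neither line. Hence

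ratio of odds ratios = (MC-NET-JITAI effect) × k.

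The values below are assumed, with a true MC-NET-JITAI effect of 1 and constant control odds:

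| Level shift (OR) | k | Ratio of odds ratios | Follow-up-only OR |
|---|---|---|---|
| 1.25 | 1 | 1.00 | 1.25 |
| 1.5 | 1 | 1.00 | 1.5 |
| 2 | 1 | 1.00 | 2 |
| 1 | 1.25 | 1.25 | 1.25 |
| 1 | 1.5 | 1.5 | 1.5 |

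A stable level difference cancels; k does not. A combined GLMM read as a follow-up comparison, without an arm-by-time term, would also carry the level difference.

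**4. How much a given k would matter.** Assume 237 and 400 independent pairs, 19% discordance in both groups, an even split of discordant pairs and an inert MC-NET-JITAI. Discordant pairs number 237 × 0.19 = 45 and 400 × 0.19 = 76.

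SE of the log ratio = sqrt(2/22.5 + 2/38) = 0.376

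Rejection probability, one-sided 2.5% = 1 - Φ(1.96 - ln(k)/0.376)

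| k (assumed) | Rejection probability |
|---|---|
| 1/1.2 | 0.7% |
| 1 | 2.5% |
| 1.2 | 7.0% |
| 1.3 | 10.3% |
| 1.5 | 18.9% |

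With an inert intervention, k can only be a difference in background trend (or in reaction to the survey). Greater responsiveness acts only if MC-NET-JITAI does something; it then multiplies the effect. A ceiling would give k below 1.

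**The case against.** The strongest case against the point has five parts.

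- **Enrollees are new people.** General Information requires this, and Study Population excludes embedded-study and snowball participants. Door-to-door staff also work "skipping those homes where current or past Phase II embedded study participants live". This stands: Phase II exposure of new enrollees is mainly spillover. It does not remove community-level exposure, since Phase I worked through communities and was measured at population level.
- **The ratio of odds ratios compares change.** This also stands, as step 3 shows. A reader might infer that the contrast measures accumulated Phase I to III exposure instead of MC-NET-JITAI. The documents do not support that, because earlier effects equally present at baseline and follow-up cancel.
- **PBGs are matched on testing and vaccination rates.** This could bear on a ceiling, but the date of the matching data is not given, and matching on rates does not equalise treatment history.
- **The earlier phases had a different main outcome.** Their primary outcome was community-level testing, mainly by PCR; Phase III's is individual antigen testing. The two overlap without being the same, which weakens any presumption of strong carry-over. Existing organisational networks are also a deliberate part of the Phase III approach, so they are not purely a nuisance.
- **The balance sentence reports a past fact.** It does, but it presents that fact as an advantage of the Phase III design.

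Two other inferences go too far. The mention of current Phase II participants among homes to skip does not establish that Phase II activity was still running there. The scale-up sentence does not itself name unexposed communities; it is simply unrestricted.

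**Conclusion.** The point holds as a limit on attribution. Arm and earlier community-level exposure are completely aliased, and the cited randomisation does not balance the arms for the MC-NET-JITAI contrast. The planned ratio of odds ratios estimates the MC-NET-JITAI effect multiplied by an unknown factor k.

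The documents give neither the direction nor the size of k. The rejection rates of 0.7% to 18.9% for k from 1/1.2 to 1.5 are illustrations under the stated assumptions. They are not estimates of this trial's error rate.

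Cancellation of the level difference assumes that it is stable on the log-odds scale and that baseline testing is comparable between groups. Phase III excludes anyone tested in the past 30 days, and the documents do not say whether the historical controls met the same rule. The effect on the control contrast matters because that contrast is the stated primary objective, even though the sized hypothesis is the within-cohort comparison.

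**What to change.** 1. In Study Design, withdraw the statement that the earlier randomisation gives balanced arms for Phase III.
2. In Objectives and Statistics, state that the control contrast estimates MC-NET-JITAI delivered in previously exposed communities versus usual practice in unexposed ones. Say that carry-over in the 8-week change, and interaction with earlier exposure, cannot be separated from it.
3. In General Information, limit the scale-up conclusion accordingly.
4. In Statistics, specify the arm-by-time term as the control contrast in the combined GLMM, so that a stable level difference cancels there as well.

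Two descriptive additions are optional: the pre-post effect by known prior arm, and Phase II baseline testing by intervention and control pool. Neither estimates the bias. The first has no unexposed stratum. The second shows only a level difference, which already cancels in the ratio of odds ratios. A new survey item on earlier contact would have no counterpart in the historical controls.

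The cost is protocol and SAP wording and one model term, with no added enrolment. The downside is a narrower claim.

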### Control Arm:

**Control PBGs:** Since we are utilizing a historical control study design, we are not recruiting any new control participants for this Phase III main study. Instead, we will analyze the survey data already collected from the Phase II embedded study control participants.

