## Statistics

**Statistical Analysis - Main Study Primary Outcomes.** We will conduct a series of analyses regarding the primary outcome variable - testing for COVID-19. First, we will conduct McNemar's test on data from the prospective cohort only. In addition to the test p-value, the odds ratio of COVID-19 testing for post-intervention versus baseline will be evaluated to assess the intervention effect. Second, based on both the prospective cohort and historical controls, we will find inferences for the ratio of odds ratios for intervention versus control. Third, using the prospective cohort, we will build a multi-level generalized linear mixed model (GLMM) including time as a fixed effect factor to evaluate intervention effect. Multiple random effects will be specified to account for the hierarchical structure of persons nested within PBGs nested within regions. Additionally, we will test variables such as individual demographics and baseline measures of rapid testing uses and include significant variables as the fixed effect factors. We will also test the PBG-level of Social Determinants of Health (SDOH) (e.g., % of minority, % of people with no insurance) to investigate the SDOHs as a potential effect modifier on the intervention effectiveness. We will also compute various network measures based on personal networks and organization affiliation patterns associated with COVID-19-related outcomes. Finally, we will build a GLMM to data of both the prospective cohort and historical controls. We will specify proper random effects to account for hierarchical nesting structure.

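### The announced matching of block groups is not carried into either analysis that compares the intervention with the historical controls

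*Combined protocol and SAP*

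**What the plan says.** The Objectives section has one primary objective: effectiveness of the intervention against a historical control group.

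Study Design gives two reasons to regard the groups as comparable. Phase III "takes advantage of the fact that these communities were randomized to conditions using methods to ensure balanced arms", and the intervention PBGs are to be matched: "they will be matched to the comparison PBGs on variables such as size, vaccination and testing rates, and the disparities index". It gives no algorithm, ratio, tolerance or date of measurement.

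On which PBGs contribute:
- Study Design: "During Phase II recruitment, we identified PBGs where recruitment was not feasible due to various factors", with no arm named, and "Recruitment in Phase III will occur only in PBGs where it is feasible to return".
- Study Design: "Among the 40 PBGs in the control arm, all remain in the control group".
- General Information, on Phase II: "A sample of the control PBGs was randomly selected from across the three study regions and assigned to the control condition".
- Control Arm: "we are not recruiting any new control participants for this Phase III main study". The 400 controls are Phase II control participants with both surveys.

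Statistics lists two analyses that use both groups. One is inference on the ratio of odds ratios, with no covariates named. The other is introduced by "Finally, we will build a GLMM to data of both the prospective cohort and historical controls" and specifies only random effects for the nesting.

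**The concern.** The protocol claims balance at the design stage but does not use it in the analysis. The two analyses that answer the primary objective do not condition on matched sets, and they do not adjust for PBG size, PBG vaccination rate, PBG testing rate or the disparities index.

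Matching is done on areas, while the comparison is made on people. Phase II enrolled by systematic sampling with a random start. Phase III enrols by convenience, at homes and through community organisations, and only in PBGs that can be revisited. The analysis set is those who complete follow-up, and the plan allows for 45% loss. Each step changes how much weight a PBG carries among the analysed participants.

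At stake is whether a difference between the groups in change from baseline can be attributed to the intervention, or partly reflects the mix of areas from which participants came.

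**Working it through.** **1. The plan's own figure, and what it covers.** Inputs from the sample size section: discordance 0.19, odds ratio 2.5, one-sided alpha 0.025, power 80%, loss 45%.
- Share of discordant pairs that are favourable: 2.5/3.5 = 0.714.
- Difference in proportions: 0.19 × (2.5 − 1)/(2.5 + 1) = 0.0814, stated as 8%.
- Power of the exact one-sided McNemar test with 237 completers, averaged over the number of discordant pairs: 0.8001. The stated 237 reproduces.
- Enrolment: 237/(1 − 0.45) = 430.9, rounded up to 431, as stated.

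This calculation uses only the prospective cohort. No control, PBG or matching variable enters it, so it neither supports nor weakens the present point.

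**2. Where the matching variables appear.**

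| Element | Where it is used | Uses controls? | Matching variable or matched set? |
|---|---|---|---|
| PBG matching | Study Design | Yes, as a design step | Yes |
| McNemar test | Statistics, first analysis | No | No |
| Ratio of odds ratios | Statistics, second analysis | Yes | None named |
| Demographics and baseline rapid-test use, kept if significant | Statistics, described with the third analysis (prospective-cohort model) | No | No |
| PBG-level social determinants, as effect modifiers | Same place | No | Possible overlap with the disparities index only |
| Combined mixed model | Statistics, final analysis | Yes | None named; random effects only |

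**3. Why matched areas need not give balanced participants.** Let x_j be a matching variable in PBG j, and n_j the number of analysed participants from it. The mean of x among participants in a group is Σ n_j x_j / Σ n_j. Matching acts on the x_j. The weights n_j come from recruitment and retention, and the documents fix them in neither group. The weighted means can differ even when the PBGs match well.

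**4. What an imbalance does to the contrast.** Suppose the log odds of testing for person i in group g (0 = control, 1 = intervention) at time t (0 = baseline, 1 = follow-up) is

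a_i + t × (c + θg + βx).

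Anything constant over time sits in a_i and largely drops out of the change. If x is omitted, the group-by-time term estimates approximately θ + βδ, where δ is the difference between groups in mean x among those analysed. The ratio of odds ratios is then multiplied by about exp(βδ). A main effect of x does not remove this, because β acts on the change. The term needed is x by time.

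**5. Size.** The documents give no value for β or δ, no number of contributing PBGs, no matching ratio and no intraclass correlation. Neither exp(βδ) nor an adjusted result can be computed.

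**The case against.** The strongest case against the point has five parts.

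- *The PBGs were randomised by minimisation and will be matched again, so adjustment is optional.* This holds for the areas as randomised. It does not extend to a convenience sample of completers from a feasible subset.
- *Time-constant differences cancel in the ratio of odds ratios.* This is largely true and narrows the point: only differences in change linked to a matching variable remain.
- *Statistics does name covariates, and the combined model is described too briefly to show that they are left out.* They are described with the prospective-cohort model, and there the area-level terms serve as effect modifiers. PBG size and PBG testing and vaccination rates are not named in that section. Overlap between the disparities index and the social determinants cannot be excluded.
- *The sized hypothesis needs no controls.* This is correct, and that test is unaffected. But it has no comparator and cannot by itself answer the stated objective.
- *Four area-level covariates with interactions may be too many.* This stands if few PBGs contribute, and the fix allows for it.

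A reader might also infer something stronger: that the matching is broken because infeasible PBGs are dropped from the intervention side while every control PBG is kept. The text looks asymmetric, since the Phase III feasibility limit can act only where people are being recruited. It does not establish that reading, for three reasons. Infeasibility was found during Phase II with no arm named, and the controls were themselves recruited then, so an unworkable control PBG may have supplied few or none. The order of matching and exclusion is not stated, and matching done after exclusion would be intact. No pairs or sets are described, so a control need not have a particular partner that was lost.

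**Conclusion.** The point holds as an omission. The plan announces matching of PBGs and gives it no role in either analysis that addresses the primary objective. Because recruitment and completion determine who is analysed, balance between areas cannot be assumed to be balance between participants.

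The conclusion rests on reading Statistics as written, without supplying covariates that it does not list for the between-group models. Bias arises only if a matching variable is related to change in testing and differs between the analysed groups; both are plausible, and the documents establish neither.

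No size can be given. A reader might want a number: an assumed slope of 0.5 in the log odds of change per SD, with an imbalance of 0.3 to 0.5 SD, gives exp(0.15) = 1.16 to exp(0.25) = 1.28. All of those inputs are invented, so these are not estimates for this trial. The claim that matching fails on one side only is not supported.

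**What to change.** 1. In the combined mixed model, pre-specify a set of PBG matching variables (size, vaccination rate, testing rate, disparities index) as fixed effects, each with a time interaction, next to the group-by-time term. State the measurement date of each, before the participant's baseline.
2. Obtain the ratio of odds ratios from a model with the same terms. In a conditional logistic model stratified by person, the main effects drop out and only the time interactions are needed. Report the adjusted ratio beside the unadjusted one.
3. State how and when PBGs are matched, whether before or after feasibility exclusions, and which PBGs on each side contribute participants.
4. Reconcile General Information, where a sample of control PBGs was drawn for Phase II, with Study Design, where all 40 remain in the control group.
5. Only if matched sets actually exist, add a sensitivity analysis limited to controls from PBGs whose matched intervention PBG was recruited. Without sets it cannot be run.

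The cost is mainly wording, since the variables must be held for the matching to be done. The models gain a few parameters and the interval becomes slightly wider. If few PBGs contribute, reduce the covariate set in advance, before outcome data are examined. The restricted analysis, if feasible, would lose some controls.
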